4.0 INTRODUCTION

This statistical analysis plan (SAP) provides a more technical and detailed elaboration of the statistical analyses of the efficacy and safety data as outlined and/or specified in the final protocol amendment of Study MT10109L-005 (version dated Oct 2020). Specifications of tables, figures, and data listings are contained in a separate document.

[figure not shown]
Study MT10109L-005 is a Phase 3, multicenter, randomized, double-blind, placebo-controlled, parallel-group study. Participants are adults at least 18 years of age with moderate to severe glabellar lines (GL) at maximum frown and Lateral Canthal Lines (LCL) at maximum smile. The severity of GL and LCL will be assessed based on Facial Wrinkle Scale (FWS) scores, ranging from none (0) to severe (3).

[figure not shown]
The length of this study will be approximately 12 months.

[figure not shown]
[REDACTED]

[figure not shown]
After the first treatment on Day 1, all participants will be evaluated for safety and efficacy at follow-up visits occurring on Day 7, 14, 30, 60, 90, 120, 150, 180, 210, 240, 270, 300, 330, and 360. Participants can receive a retreatment (Treatment 2) of MT10109L 20 U, 44 U, or placebo if retreatment criteria are met at the Day 180 visit.

[REDACTED]

5.0 **OBJECTIVES**

The objectives of this study are to evaluate the safety and efficacy of MT10109L versus placebo in the treatment of participants of GL with or without concurrent treatment of LCL.

6.0 PARTICIPANT POPULATIONS**6.1 INTENT-TO-TREAT POPULATION**

The intent-to-treat (ITT) Population will consist of all randomized participants. Efficacy analyses for US FDA will be based on the ITT population.

**6.3 SAFETY POPULATION**

The safety population will consist of all participants who received at least 1 injection of study intervention.

7.0 PARTICIPANT DISPOSITION

The number and percentage of participants in the 3 study populations (ITT, [REDACTED] safety) will be summarized by treatment group and overall; the number of participants screened and randomized will be summarized by study center.

The number of participants screened will be summarized overall. The number and percentage of participants who were randomized, treated, or who completed the study and prematurely discontinued will be presented for each treatment group and pooled across treatment groups. A frequency table showing participant disposition (continuing, entered to the next cycle, completed, discontinued) will also be provided for all analysis populations for each treatment cycle.

Tabulation of the numbers and percentages of participants in each exit status category (i.e., adverse event, pregnancy, lost to follow-up, personal reasons, protocol violations and other) will be provided for each treatment group for entire study and by treatment cycle for all analysis populations. Discontinued participants will be listed along with the corresponding reason(s) for early withdrawal from the study.

8.0**DEMOGRAPHICS AND OTHER BASELINE CHARACTERISTICS**

Demographic parameters and baseline characteristics will be summarized by treatment group for ITT [REDACTED]. Continuous variables will be summarized by number of participants and mean, SD, median, minimum, and maximum values. Categorical variables will be summarized by number and percentage of participants.

Demographic parameters include age, age group (< 65 and \geq 65), race, ethnicity and sex.

Baseline characteristics include weight, height, body mass index (BMI, calculated as weight [kg]/height[m]²), FWS scores of GL severity at maximum frown and at rest (assessed by investigators and participants), LCL severity at maximum smile and rest (assessed by investigators only), [REDACTED]

[REDACTED]. The distribution of the baseline characteristics will be summarized by treatment group.

The number and percentage of participants with abnormalities in medical and surgical histories in each system organ class (SOC) and preferred term (PT) will be summarized by treatment group for the ITT population.

Prior medications include all medications taken any time prior to the Day 1 baseline visit, whether or not medication is continuing beyond the Baseline Visit.

Concomitant medications encompass all medicinal products that the participant was taking prior to the Day 1 baseline visit which are ongoing at the visit, in addition to all medications that have a start date on or after the Day 1 visit date.

WHODrug Global B3 202003 will be used to classify prior and concomitant medications by therapeutic class and drug name.

Both prior and concomitant medications will be coded by drug name and therapeutic class. The use of prior and concomitant medications will be summarized by drug class and drug name in each treatment group for the ITT [REDACTED].

9.0**EXTENT OF EXPOSURE AND TREATMENT COMPLIANCE****9.1****EXTENT OF EXPOSURE**

Participants' exposure to study intervention will be summarized by total duration of treatment exposure and by cycle [REDACTED]
[REDACTED] and by number of treatments received.

10.0 EFFICACY ANALYSES

For US FDA, the primary and secondary efficacy analyses will be based on the ITT population. For EU regulatory agencies, the primary and secondary efficacy analyses will be based on the mITT population. Other efficacy analyses will be based on the ITT population.

Missing values for the primary measures will be imputed using multiple imputation methods up to Day 180 for Treatment Cycle 1.

The evaluation of the equality of the proportions of responders will be based on Cochran-Mantel-Haenszel (CMH) test stratified by investigator-assessed baseline GL severity at maximum frown.

10.1 PRIMARY EFFICACY PARAMETER(S)

US FDA

For US FDA, the composite primary efficacy endpoint is the proportion of participants with a ≥ 2 -grade improvement from baseline on the FWS according to both the investigator- and participant-rated assessments of GL severity at maximum frown at Day 30 of Treatment Cycle 1.

[figure not shown]
The primary analysis will be performed on the ITT population.

[figure not shown]
The following hypothesis will be used to compare the MT10109L groups with placebo:

- Null hypothesis: MT10109L 20 U and placebo are equally effective in reducing GL severity at maximum frown as measured by the proportion of responders with a \geq 2-grade improvement from baseline based on both the investigator-rated and participant-rated FWS at Day 30 of Treatment Cycle 1.
- Alternative hypothesis: MT10109L 20 U and placebo are not equally effective in reducing GL severity at maximum frown as measured by the proportion of responders with a \geq 2-grade improvement from baseline based on both the investigator-rated and participant-rated FWS at Day 30 of Treatment Cycle 1.

Analyses of the secondary efficacy variables will be performed for all study visits using observed data, with the primary time-point at Day 30 of the Treatment Cycle 1 [REDACTED]

[REDACTED]

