9.3. Populations for Analyses

Primary and secondary efficacy analyses for US FDA will be performed on the ITT population, consisting of all randomized participants.

The safety analyses will be based on the safety population, which will include all participants who receive at least 1 injection of study intervention. All safety analyses will be performed with participants analyzed by their actual treatment or regimen received.

MT10109L

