9.4.1.2. Primary Analyses

The primary efficacy analysis will be based on the comparison of GL efficacy for MT10109L 20 U versus placebo at the primary timepoint of Day 30 of the first treatment period. The evaluation of the equality of the proportions of responders will be based on CMH test stratified by investigator-assessed baseline GL severity at maximum frown. Relative risk and 95% CI for relative risk will be presented. Missing values will be imputed up to Day 180 using multiple imputation methods.

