9.4.1.4. Secondary Analyses

All secondary variables will be evaluated for all study visits with the prespecified primary timepoint given below, except for duration of treatment effect.

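### US secondary efficacy is assigned to all randomized participants, but the visible SAP analyses it on observed data while the primary measures are multiply imputed to Day 180

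*SAP*

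**What the plan says.** **Who is to be analysed.** Protocol 9.3: "Primary and secondary efficacy analyses for US FDA will be performed on the ITT population, consisting of all randomized participants". SAP 10.0 agrees: "For US FDA, the primary and secondary efficacy analyses will be based on the ITT population". SAP 6.1 defines that set: "The intent-to-treat (ITT) Population will consist of all randomized participants". The EU analyses differ: "For EU regulatory agencies, the primary and secondary efficacy analyses will be based on the mITT population". The mITT definition is not in the public text, so this point concerns the US analyses.

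**What happens to missing values in the primary.** Protocol 9.4.1.2: "Missing values will be imputed up to Day 180 using multiple imputation methods". SAP 10.0: "Missing values for the primary measures will be imputed using multiple imputation methods up to Day 180 for Treatment Cycle 1".

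**What happens to missing values in the secondaries.** SAP 10.1, in the part written for US FDA: "Analyses of the secondary efficacy variables will be performed for all study visits using observed data". It names Day 30 of Cycle 1 as the primary time-point, and redacted text follows. Protocol 9.4.1.4 says only this in its visible text: "All secondary variables will be evaluated for all study visits with the prespecified primary timepoint given below, except for duration of treatment effect". That sentence carries no missing-data rule.

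**The concern.** At Day 30 of Cycle 1 the plan would report a primary result covering everyone randomized and secondary results covering only those with a value at that visit. The two rest on different analysed sets and different missing-data assumptions, although some secondaries may come from the same FWS ratings.

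An observed-case responder comparison is sound if, within arm and baseline-severity stratum, having a missing value is unrelated to response. The visible text neither states nor tests that assumption for the secondaries. It could fail: Protocol section 7 includes lack of efficacy among its terms for discontinuation, and SAP 11.8 anticipates COVID-19 effects on visits, including missed and audio-only ones, but in the visible text only lists them.

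Observed-case analysis of Day 30 also ignores what a participant showed at Days 7 and 14. Multiple imputation can use those values, so its missing-data assumption is easier to defend. What is at stake is whether the US secondary estimates describe the population to which the plan assigns them.

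**Working it through.** **1. Reproduce the plan's own figure.** The protocol synopsis gives 375 enrolled, 318 completers and 15% dropout.

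- 318 / (1 − 0.15) = 374.1, rounded up to 375. This matches.
- 375 − 318 = 57 participants are expected not to complete.

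The 15% is loss over the whole study to Day 360. Neither document gives a figure for Day 30 in its public text.

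**2. Set the rules side by side (US, Day 30 of Cycle 1).**

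| | Primary | Secondary |
|---|---|---|
| Declared population | all randomized | all randomized |
| Missing value | multiply imputed | not imputed; observed data |
| Participants contributing | about 375 | those with a Day 30 value |

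Taking 2% to 10% missing at Day 30 as an assumed range, 375 × 0.02 = 7.5 to 375 × 0.10 = 37.5, so about 8 to 38 participants across the three arms would not contribute to a Day 30 secondary analysis.

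**3. Illustrate the effect on one arm's responder rate.** Let m be the share missing, p the rate among those observed and r the rate among those missing. The all-randomized rate is p(1 − m) + rm, so observed-case overstates it by m(p − r). Assume p = 70% and r from 0 to 40%. Both are assumptions, since the planned responder rates are not public.

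| m | r = 40% | r = 0 |
|---|---|---|
| 2% | 0.02 × 30 = 0.6 points | 0.02 × 70 = 1.4 points |
| 5% | 0.05 × 30 = 1.5 points | 0.05 × 70 = 3.5 points |

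Taking r below p fixes the direction in advance. If missing participants respond more often than observed ones, the sign reverses.

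**4. Illustrate the effect on the treatment difference.** Assume observed rates of 65% and 5% (difference 60 points) and 5% missing in each arm.

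- All missing are non-responders: 65 × 0.95 − 5 × 0.95 = 61.75 − 4.75 = 57 points.
- Least favourable (active missing fail, placebo missing respond): 61.75 − (4.75 + 5) = 52 points.
- Most favourable (the reverse): (61.75 + 5) − 4.75 = 62 points.

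The observed difference of 60 lies inside the range 52 to 62, so the direction is not determined.

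**5. What these figures do not measure.** They compare observed-case with a hypothetical true all-randomized rate. They do not show what multiple imputation would change. Standard imputation assumes data are missing at random, and it moves the estimate only as far as other recorded data predict the missing response.

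**The case against.** The strongest reply is that the plan made an explicit, prespecified choice. ITT settles who is eligible and under which assigned arm, whereas observed data is a missing-data rule, and the two can coexist. A reader might infer that the documents contradict each other. They do not, and that part of the reply stands. It does not answer why the secondaries take the less protected rule when imputed scores for the primary measures already exist to Day 180.

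Second, much of the efficacy section is withheld, and redacted text directly follows the quoted sentence. A reader might infer that observed-case is the only analysis of the secondaries. The documents do not support that: a supplementary imputed analysis cannot be excluded. SAP 10.0 also speaks of primary measures rather than the primary endpoint, so secondaries built on the same scores might be meant to share the imputation. The visible sentence in 10.1 makes no such exception, and a clear statement is needed either way.

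Third, several stronger arguments are tempting and fail:

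- Putting 15% missing into step 3 gives 0.15 × 30 = 4.5 to 0.15 × 70 = 10.5 points. That is full-study dropout and nothing supports it at Day 30, where loss is probably well below it.
- Missingness that differs by arm alone does not bias the rates or their difference. It must also be related to response within arm.
- Both documents cite a chapter on gatekeeping. One might infer that the secondaries carry formal claims, but the amendment history mentions a condition for testing the 44 U group, so the citation may concern that step.
- Lack of efficacy appears in a generic list in the protocol and is absent from the SAP 7.0 exit-status categories. It makes response-related loss plausible, no more.

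**Conclusion.** The point holds as a weakness in the choice of analysis that should be corrected. On the visible text, the US secondary analyses leave out participants without a value at the visit, although the declared population is everyone randomized, and they do so at the same Day 30 at which the primary measures are imputed.

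The size and direction of any bias cannot be derived from the public text. Under the assumed 70% observed response, 0-40% response among missing participants, and 2-5% missing, the single-arm overstatement is about 0.6 to 3.5 points, and imputation would recover only part of it. The Day 30 effect is therefore likely to be modest. The case for change rests mainly on matching the analysis to the declared population, using the Day 7 and Day 14 data, and making the missing-data assumption explicit and testable.

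**What to change.** In SAP 10.1, for the US analyses:

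- **Responder secondaries derived from the FWS measures imputed for the primary, at Cycle 1 visits to Day 180:** derive the endpoint from the imputed scores and use the primary's multiple-imputation and CMH combination as the main analysis. Keep observed-case as a sensitivity analysis.
- **Visits after Day 180:** keep observed-case as the analysis and label it so.
- **Secondaries that are not FWS-based or not binary:** use multiple imputation with a model suited to the endpoint, or state plainly that the result is observed-case. CMH and the existing imputed datasets may not fit these.
- **All secondaries:** report the number analysed by arm and visit.

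The cost is SAP wording and some extra programming, more where an endpoint needs its own imputation model. Estimates may become slightly less favourable. Protocol 9.4 requires the SAP to be final before database lock and unblinding, so the change belongs before that point. If the redacted text already provides this, the sponsor need only confirm it.

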11.0 SAFETY ANALYSES

The safety analysis will be performed using the safety population. The safety parameters will include adverse events (AEs), [REDACTED] vital signs, Electrocardiogram (ECG), Hematology and Chemistry laboratory and immunogenicity analyses. For each safety parameter of the vital sign, ECG, Hematology and Chemistry laboratory parameters, the last non-missing safety assessment before the first dose of study intervention will be used as the baseline for all analyses of that safety parameter. Continuous variables will be summarized by number of participants and mean, SD, median, minimum, and maximum values. Categorical variables will be summarized by number and percentage of participants.

11.1 ADVERSE EVENTS

AEs will be coded from the verbatim text into preferred term (PT) and the primary system organ class (SOC) by using the MedDRA dictionary. In general, adverse events (AEs) data will be analyzed and presented for:

1. TEAEs: An adverse event will be considered a treatment-emergent adverse event (TEAE) if: 1) The adverse event began on or after the date of the first study intervention; or 2) The adverse event was present before the date of the first study intervention, but increased in severity or became serious on or after the date of the first study intervention. An adverse event that occurs more than 30 days after the study exit will not be counted as a TEAE.

[REDACTED]

Per case report form instructions, a new AE record will be created with a new AE onset date for any AE that worsens. Therefore, TEAEs can simply be identified as those AEs with a recorded onset date on or after the date of the first study intervention and within 30 days after the study exit.

In each of the analysis periods (entire study, or by treatment cycle), a specific TEAE will only count once per participant, associated with its worst severity during the time period of interest. Unless stated otherwise, the method of analyses described in this section will be applied to each of the screening/baseline and study intervention periods.

Adverse events will be summarized by treatment group for the entire study and by treatment cycle in descending order of incidence rate.

Three incidence rate tables will be presented for summarizing all TEAEs:

- 1) by descending order of incidence rate
- 2) by primary SOC and PT
- 3) by SOC, PT, and severity.

Serious TEAE and treatment-related TEAE will be summarized by primary SOC and PT for entire study. Treatment-related TEAE will also be summarized by related to study drug or related to study procedure. TEAE leading to study discontinuation will be summarized by primary SOC and PT for entire study

A participant listing will be generated for all AEs, SAEs, treatment-related AEs and AEs leading to study discontinuation.

All AEs associated with PDSOT will be tabulated by SOC, PT, and treatment group; in addition, all PDSOT AEs will be listed by participant.

11.2 CLINICAL LABORATORY PARAMETERS

Study baseline is defined to be the data measured before dosing on Day 1. Descriptive statistics (n, mean, standard deviation, minimum, median, and maximum) for clinical laboratory values at baseline, and change from baseline at post-baseline visits will be summarized, in SI units (System of International Units), for all continuous clinical laboratory parameters specified below.

The clinical laboratory parameters include the following:

Hematology: Hemoglobin, hematocrit, red blood cell count (RBC), RBC morphology, white blood cell count (WBC), neutrophils, lymphocytes, monocytes, basophils, eosinophils, and platelets

Blood Chemistry: glucose, creatinine, urea nitrogen, total bilirubin, albumin, aspartate aminotransferase (AST), alanine aminotransferase (ALT), alkaline phosphatase, uric acid, sodium, potassium, bicarbonate (carbon dioxide content), chloride, phosphorus, calcium, magnesium, and total protein.

11.3 VITAL SIGNS

[figure not shown]
Study baseline is defined to be the data measured before dosing on Day 1. Baseline and change from study baseline data on blood pressure (mm Hg), pulse rate (beats/min) and respirations (breaths per minute) will be summarized as descriptive statistics for each time point and each visit for each treatment group.

11.4 ELECTROCARDIOGRAM

Descriptive statistics for ECG parameters (eg, heart rate, PR interval, RR interval, QRS duration, QT interval, corrected QT [QTc] intervals) at baseline, and changes from baseline at all post-baseline timepoints will be presented for all participants in the Safety Population. For each parameter, only participants who had both baseline post-baseline assessments will be included in the summary.

Data listings which include ECG basic parameters and ECG abnormalities will be produced.

11.7 PREGNANCY TESTS

Urine pregnancy tests are performed prior to treatment and at exit visit for females of childbearing potential. Participants with positive pregnancy test results will be listed by treatment group, including urine sample collection date, and days since most recent treatment.

11.8 IMPACT DUE TO COVID-19

Participants discontinued related to COVID-19 will be listed.

The description of impact to visit assessment due to COVID-19 (missed, remote audio visit, etc.) will be listed.

For participants affected by COVID-19, their COVID-19 status, COVID-19 supplemental signs and symptoms will be listed.

12.0 **INTERIM ANALYSIS**

No interim analysis is planned for this study.

13.0 DETERMINATION OF SAMPLE SIZE

[figure not shown]
Approximately 375 participants will be randomized

14.0 STATISTICAL SOFTWARE

Statistical analyses will be performed using version 9.3 (or newer) of SAS on a Linux operating system.

If there are values from multiple visits in a given window, the value collected from the visit closest to the target day will be used

15.5 REPEATED OR UNSCHEDULED ASSESSMENTS OF SAFETY PARAMETERS

If a participant has repeated assessments before the start of the first treatment, the results from the final nonmissing assessment made prior to the start of the study intervention will be used as baseline. If end-of-study assessments are repeated or if unscheduled visits occur, the last nonmissing postbaseline assessment will be used as the end-of-study assessment for generating summary statistics.

15.6 MISSING SEVERITY ASSESSMENT FOR ADVERSE EVENTS

If severity is missing for an AE that started before the date of the first dose of study intervention, an intensity of mild will be assigned. If severity is missing for an AE that started on or after the date of the first dose of study intervention, an intensity of severe will be assigned. The imputed values for severity assessment will be used for the incidence summary; the values will be shown as missing in the data listings.

15.7 MISSING CAUSAL RELATIONSHIP TO STUDY INTERVENTION FOR ADVERSE EVENTS

If the causal relationship to the study intervention is missing for an AE that started on or after the date of the first dose of study intervention, a causality of yes will be assigned. The imputed values for causal relationship to study intervention will be used for the incidence summary; the values will be shown as missing in the data listings.

